### 2.4 Aims and objectives

This is a non-commercial, UK, multi-centre, parallel group, pragmatic, randomised controlled trial that aims to determine the clinical and cost effectiveness of early APRV compared to conventional lung protective IMV in patients with moderate-severe AHRF.

### 2.4.1 Primary objective

To determine the effectiveness of APRV for reducing the duration of IMV compared to conventional lung protective ventilation.

### 2.4.2 Secondary objective

To determine the effect of APRV compared to conventional lung protective ventilation on the following:

- All-cause mortality at 2 and 6 months
- First extubation
- Reintubation
- Use of non-invasive ventilation following extubation
- CCU and hospital length of stay
- Serious adverse events up to hospital discharge
- Health related quality of life (EQ-5D-5L) at 2 and 6 months after randomisation
- Acute health care use at 2 and 6 months after randomisation
- Within-trial cost-utility analysis from an NHS hospital care perspective (see Section 6.5).

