### 1.2 Existing knowledge

APRV is one of three interventions not currently standard of care in the NHS (others are corticosteroids and non-invasive ventilation) with evidence of potential effectiveness which requires further study.[7] Four recent systematic reviews (totalling 10 studies, 519 participants) on APRV[8-11] suggest APRV reduces time spent on the ventilator and mortality. One review[9] (7 trials, 405 participants) found an increased number of ventilator free days at day 28 with APRV compared to conventional ventilation (mean difference 5.4 days). Three reviews [9, 10, 12] report a mortality benefit favouring APRV while two report improved gas exchange but no difference in mortality and ventilation free days[11, 13]. One subsequent trial (65 participants)[14] reported no difference in mortality or IMV duration, although median CCU length of stay was 5 days shorter in the APRV arm.

igure 1: Meta-a	analys	nalysis of ventilation duration (unpublished data)						Mean Difference IV, Random, 95% CI	
		APRV			Control			Mean Difference	•
Study or Subgroup	Mean	SD	Total	Mean	SD	Total	Weight	IV, Random, 95% Cl	-
Ibarra-Estrada 2022	9	5.925	45	10	5.185	45	19.9%	-1.00 [-3.30, 1.30]	•
Kucuk 2021	9.84	8.033	32	13.52	12.826	33	14.4%	-3.68 [-8.87, 1.51]	
Maxwell 2010	10.49	7.23	31	8	4.01	32	18.9%	2.49 [-0.41, 5.39]	
Ota 2009	17	17	17	23	20	40	7.2%	-6.00 [-16.18, 4.18]	
Putensen 2001	15	2	15	21	2	15	21.1%	-6.00 [-7.43, -4.57]	
Zhou Y 2017	8	6.67	71	15	11.11	67	18.5%	-7.00 [-10.08, -3.92]	-100 -50 0 50 10
Total (95% CI)			211			232	100.0%	-3.26 [-6.60, 0.09]	Favours [APRV] Favours [control]
Heterogeneity: Tau  =	13 23 0	$hi^2 = 37$	08 df	$= 5 (P \leq$	0.00001	$  ^{2} = 8$	7%		

Heterogeneity: Tau\* = 13.23; Chi\* = 37.08, df = 5 (P < 0.00001); I\* = 87% Test for overall effect: Z = 1.91 (P = 0.06)

To obtain data on IMV duration, we conducted a meta-analysis of the studies reporting IMV duration (Figure 1) and we found that APRV was associated with a mean reduction in IMV duration of 3.3 days (95% CI -6.6 to 0.1 days) (I=87%). However, evidence certainty is low, due to methodological limitations and trial heterogeneity. Most of the trials are small and few primarily recruit patients with moderate AHRF early in the course of IMV. Furthermore, no study to-date has reported on cost-effectiveness of APRV.

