### 1.3 Hypothesis

Our primary hypothesis is that adult CCU patients requiring IMV for moderate-severe AHRF will have a shorter duration of mechanical ventilation if ventilated with APRV compared to usual care.

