### 4.1 Pre Specified Complications

As per the CoReCCT Safety Reporting Flowchart, adverse events that 1) occur at sites between randomisation and hospital discharge and 2) are not present on the CoReCCT Exemption List, must be reviewed for their presence on the RELEASE Pre-Specified Complications List as given below.

Pre-Specified Complications List (that occur up to Day 10 post randomisation)

Barotrauma (including pneumothorax, pneumomediastinum, subcutaneous emphysema)

Hypotension requiring new vasopressors or increase in vasopressors of more than 0.2 microgram/kg/min

As per the CoReCCT Safety Reporting Flowchart, if the event is present on the Pre-Specified Complications List and occurred up to Day 10 post-randomisation, the event must be recorded on the appropriate CRF as an outcome and does not need to be reported on an SAE form. Pre specified complications which occur beyond Day 10 post-randomisation will not be recorded. If the event is not on the list, it must be assessed for seriousness and the remainder of the flowchart should be followed to determine next steps.

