### 6.2.3.3 Secondary outcome analysis

In general, continuous baseline and outcome data will be summarised with descriptive statistics, including n, mean, standard deviation, median, IQR and n of missing data. We will use mixed-effects linear regression models to estimate mean treatment differences (95% CI). Categorical baseline and outcome data will be summarised with frequency counts and percentages. We will use mixed-effects logistic regression models to estimate the difference in binary outcomes between treatment groups, with odds ratios and 95% CIs reported. Survival based outcomes will be analyzed using the Cox proportional hazards model with data displayed using the Kaplan-Meier plots.

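### Serious adverse events are compared only up to hospital discharge, a window whose length treatment may change; a comparison over a common fixed window should stand beside it

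*Protocol*

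**What the plan says.** Protocol section 2.4.2 lists the safety outcome as "Serious adverse events up to hospital discharge", and the Trial Summary repeats it. The schedule in section 3.1 collects SAEs to the same end point. Section 4.1 covers events that "occur at sites between randomisation and hospital discharge". The list in section 2.4.2 also contains "CCU and hospital length of stay", so the end of the SAE window is itself an outcome.

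Section 6.2.3.3 gives analysis rules by type of outcome. For binary ones: "We will use mixed-effects logistic regression models to estimate the difference in binary outcomes between treatment groups", reported as odds ratios. It names no exposure time and does not say which rule applies to SAEs.

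Other harms have fixed windows. Under section 4.1, barotrauma and hypotension needing new or increased vasopressors are recorded as outcomes, off the SAE form, if they "occurred up to Day 10 post-randomisation". Mortality is compared at 2 and 6 months.

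On whether the window may differ by arm, section 1.3 states that patients "will have a shorter duration of mechanical ventilation if ventilated with APRV compared to usual care". Section 1.2 cites one 65-patient trial in which "median CCU length of stay was 5 days shorter in the APRV arm".

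**The concern.** An SAE on day 20 counts for a patient still in hospital and not for one who has gone home. If the arms differ in time to discharge or in mortality, they are observed for different lengths of time, and an SAE comparison to discharge mixes the risk of an event with the time over which it could be recorded. Equal daily risk could then look like a safety benefit, or a modestly higher daily risk could look like no difference. Section 1.5 says that a harmful result would lead to work to withdraw the technique from practice, so the harm comparison should be interpretable without knowing length of stay.

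**Working it through.** **The plan's own figure.** The protocol gives no expected SAE rate and no expected hospital stay. Its sample size does confirm how to read the planned effect. With medians of 9 and 7 days (section 6.1) and exponential times, the hazard ratio is 9/7 = 1.286. Freedman's formula at two-sided 5% and 90% power gives ((1.286 + 1)/(1.286 - 1))² × (1.960 + 1.282)² = 64 × 10.51, or 673 events. Then 673/0.95 = 709, against 710 stated. So 9 v 7 days is the right contrast to carry forward.

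**Model for the to-discharge window.**

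- Stay after randomisation is T = X + c. X is exponential ventilated time with rate λ = ln 2/median, so 0.0770 (control) and 0.0990 (APRV).
- c is stay after ventilation, assumed 5 to 25 days and equal in both arms.
- Daily SAE risk h is assumed constant and equal in both arms, at 0.005 to 0.02.
- Deaths are ignored at this step. There are 355 patients per arm.
- P(at least one SAE) = 1 - exp(-hc) × λ/(λ + h).

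Example with c = 10 and h = 0.01:

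- Control: 1 - 0.9048 × 0.0770/0.0870 = 19.9%.
- APRV: 1 - 0.9048 × 0.0990/0.1090 = 17.8%.
- Odds ratio: (0.178/0.822)/(0.199/0.801) = 0.87, nominally significant in about 11% of trials.

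Over h = 0.005 to 0.02:

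| c (days) | Mean window, control v APRV (days) | SAE odds ratio at equal daily risk | Nominal rejection |
|---|---|---|---|
| 5 | 18.0 v 15.1 | 0.84 | 10-18% |
| 10 | 23.0 v 20.1 | 0.87 | 8-14% |
| 15 | 28.0 v 25.1 | 0.89-0.90 | 8-12% |
| 25 | 38.0 v 35.1 | 0.91-0.92 | 7-9% |

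**A simpler check.** With a constant daily rate, a window shortened from L to L - d days leaves the count per patient unchanged when the daily rate ratio is L/(L - d). For d = 2 this is 20/18 = 1.11, 30/28 = 1.07 and 40/38 = 1.05. For d = 5 it is 20/15 = 1.33 and 30/25 = 1.20. The table implies a larger gap than 2 days because a 2-day difference in exponential medians is a difference of 2/ln 2 = 2.9 days in means.

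**Deaths.** Section 1.1 gives mortality of about 40%. Assume that patients who die are observed for 10 days, and survivors for 30 (control) or 28 (APRV). The control mean is 0.4 × 10 + 0.6 × 30 = 22.0 days. The APRV mean is:

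- at 40% mortality, 20.8 days (ratio 0.95);
- at 35%, 21.7 days (0.99);
- at 30%, 22.6 days (1.03).

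Lower mortality under APRV can therefore cancel or reverse the shortening.

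**Fixed window to Day 10, same model.** With c of 10 days or more nobody is discharged before Day 10, and the odds ratio is 1.00. With c = 5 it is 0.98 (for h = 0.01, 8.7% v 8.5%). Rejection is about 5% throughout.

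**Rate per patient-day.** If both arms had identical SAEs, all early, dividing by the mean windows for c = 5, 10 and 15 would show an excess under APRV of 18.0/15.1 = 1.19, 23.0/20.1 = 1.14 and 28.0/25.1 = 1.11. That measure is not neutral either.

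**The case against.** The strongest reply is that the protocol never assigns SAEs to logistic regression. Section 6.2.3.3 gives general rules, and section 6.2.2 leaves detail to a statistical analysis plan that is not shown and could add a rate or a fixed-day comparison. A reader might infer that an odds ratio ignoring time at risk is the stated SAE analysis, but the text does not say so. This stands. What the protocol does fix is the outcome and its window, and that window is the point here.

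A reader might also infer that APRV is meant to bring hospital discharge forward. The stated hypothesis concerns ventilation, hospital stay is only a secondary outcome, and the cited evidence is CCU stay in one small trial. Earlier discharge is a possibility, not a stated aim.

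Third, events over the whole admission are a legitimate quantity: fewer hospital days at risk is a real benefit to the patient. So rejection above 5% is a false-positive rate only if the null hypothesis is equal daily risk. This is why the to-discharge figure should stay.

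Fourth, the main ventilation-related harms and death already have fixed windows. This also stands, and it narrows the point to the remaining reportable SAEs. Which events those are depends on the CoReCCT Master Protocol, which is not shown.

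Finally, if SAEs cluster early, the days lost at the end of the stay carry few events and the effect shrinks. In that case a Day 10 comparison also loses little.

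**Conclusion.** The point holds in a limited form. The SAE outcome is observed over a patient-dependent window that treatment may alter, and the protocol states no common window beside it, so the result can partly reflect length of observation.

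At equal daily risk the odds ratio is about 0.84-0.92. That range assumes exponential ventilated time with medians of 9 and 7 days, 5-25 further days in hospital, constant daily risk of 0.5-2% and no deaths. Stay and SAE rate are assumptions, not protocol figures.

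It would be tempting to conclude that the design favours APRV or will hide harm. The documents do not support that: death also ends the window, and with mortality near 40% the direction is open. Barotrauma, vasopressor-requiring hypotension and mortality are unaffected. This is a cheap improvement, not an error that undermines the trial.

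**What to change.** Keep SAE collection to hospital discharge and keep reporting that figure. Add, in the protocol or the statistical analysis plan, a between-arm comparison of the proportion of patients with at least one SAE by Day 10 after randomisation, a window section 4.1 already uses. Base any statement on relative SAE risk on that comparison. An SAE rate per patient-day may be shown as supportive only, since its denominator is affected by treatment.

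The cost is a sentence and one further analysis. It uses SAE records already collected, provided that event dates are held. The downside is that a Day 10 window leaves out later SAEs, which is why the to-discharge figure stays beside it.

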### 2.4.3 Primary and secondary endpoints

We have included as our trial outcomes, the core outcome set for trials of interventions intended to modify IMV duration developed by members of our group.[21]

Our primary outcome is duration of mechanical ventilation in days commencing at randomisation and discontinuing at first successful unassisted breathing or death.

Unassisted breathing is defined as remaining to breathe unassisted at 48 hours with no inspiratory support or extracorporeal lung support. Duration of assisted breathing includes time receiving extracorporeal lung support, invasive mechanical ventilation and non-invasive ventilation delivering volume or pressure support ventilation; **excludes** high-flow oxygen therapy and continuous positive airway pressure.

This definition was agreed through an international consensus process, involving clinician, researcher, patient and family representatives, and industry. This primary outcome was chosen with PPI input.

Secondary outcomes are listed in section 2.4.2.

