### 2.9.2.5 Weaning APRV

Once a patient's clinical condition has improved, clinicians will follow a protocol to wean a patient using APRV that does not involve switching mode to pressure support ventilation, which is the weaning mode most commonly used as standard care.

Once improved (FiO2  $\leq$  40%, SpO2 92-95% and able to sustain spontaneously breathing at a comfortable rate (i.e., 10-30 bpm), APRV should be weaned as follows:

- 1. Progressively increase the inspiratory time ( $T_{high}$ ) by 0.5-1s steps until  $T_{High} > 6$  seconds; and wean the  $P_{HIGH}$  by in 2 cmH2O increments as tolerated to a  $P_{HIGH of}$  15 cmH2O.
  - a. Monitor for desaturation, increased work of breathing, or tachypnea
  - b. When the patient reaches a  $P_{HIGH of}$  10-12 cmH2O, patient can be transitioned to CPAP 10-12 cmH2O without pressure support (PS = 0 cmH2O) and undergo checks for extubation

Participants must continue to receive APRV until extubation to maximise the APRV "dose" received. Remember to optimise sedation to promote more spontaneous breathing.

60	P HIGH = Up or Down –Titrate by 1-2 cmH 2 O to maintain V T >4 and <10ml/kg	Monitor
Weaning	T HIGH + 0.5-1.0 s increments Every 1-2 hours until T high up to 30s Transition to CPAP Optimise Sedation to allow progressively more spontaneous breathing	
 
P0.1
 
ΔPocc
 
RSBI
 
Respiratory Pattern
 

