### 2.9.3.1 Weaning in the control arm

Weaning will be conducted according to the usual practices of the participating site (low level pressure support, CPAP or T-Piece) and may or may not include a spontaneous breathing trial. In general criteria for weaning comprise the following:

- o FiO₂ ≤0.40
- PEEP  $\leq 8 \text{ cmH}_2\text{O}$
- Patient has acceptable breathing efforts
- Systolic blood pressure > 90 mmHg without vasopressors

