### 3.1 Schedule of delivery of intervention and data collection

The following baseline, clinical, and outcome data will be collected by the local research delivery team from the electronic medical record. In brief the dataset will include:

	Baseline	Day 3	Day 7	Up to Day 10	Up to CCU discharge	Up to hospital discharge	Post-hospital discharge	
					alsonarge		2 months	6 months
Eligibility assessment	x							
Consultee agreement	x							
Baseline data collection	x							
Randomisation	Х							
Ventilator settings, sedation use, organ failure, use of rescue therapies				X				
Serious Adverse Events						x		
Primary outcome					x			
Mortality (secondary outcome)					x	x	х	x
HrQoL (secondary outcome)							х	x
Healthcare utilisation after dx							х	х
Optional blood samples	х	x	x					

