### 6.2.3.2 Primary outcome analysis

Primary outcome and the Estimand Framework

In addition to the objectives, interventions and the population already stated above, the following define the Estimand framework that will be used for the RELEASE trial, in line with the ICH E9 (R1) addendum on Estimand and sensitivity analyses in clinical trials.[23]

Variable (outcome): Our main variable (outcome) of interest is ventilation duration, from the time of randomisation to successful extubation or death. 'Successful extubation' will be defined using the core outcome set[21] definition i.e., the time point a patient is free of ventilatory (invasive or non-invasive) support for >48 hours.

Summary measure and the primary Estimand: Ventilation duration will be determined as the time of successful extubation/death minus the time from the point of randomisation (in hours/mins). The statistical analysis for this outcome will be performed using the treatment policy strategy (i.e., intention-to -treat). Statistical summaries of ventilation duration will be made using median and interquartile range (IQR). We will use a Cox proportional hazard regression model to estimate the treatment difference reporting hazards ratios and their 95% confidence intervals (CIs), using both unadjusted and adjusted estimates. We will report the mean difference with 95% CIs using linear regression.

Intercurrent events (ICEs) and strategies for handling ICEs: post-randomisation events that may affect the interpretation of the primary outcome include: (a) crossover; (ii) non-adherence (including discontinuation of treatment); and (iii) death. Rates of crossover and non-adherence will be added using the principal stratum strategy. We will use the inverse probability weighted analysis method[24] to assess the treatment effect, having taken account of these events. The composite strategy will be used to assess the effect of death, with ventilation duration. We will use the Pocock's win-ratio method[25] and also assess the interaction of ventilation duration with mortality status, bearing in mind the interaction term may not be powered to detect differences.

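### The primary outcome has two incompatible end points, and neither says how CPAP through a tube is counted; the ambiguity may not be neutral between the arms

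*Protocol*

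**What the plan says.** **First definition (Protocol 2.4.3).** The outcome is duration in days, "commencing at randomisation and discontinuing at first successful unassisted breathing or death". Unassisted breathing means "remaining to breathe unassisted at 48 hours with no inspiratory support or extracorporeal lung support". Assisted time includes extracorporeal support, invasive ventilation, and non-invasive ventilation with volume or pressure support. It "excludes high-flow oxygen therapy and continuous positive airway pressure". Section 2.9.4.2 refers back to 2.4.3 as the full definition.

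**Second definition (Protocol 6.2.3.2).** The estimand variable runs to successful extubation or death, where success is "the time point a patient is free of ventilatory (invasive or non-invasive) support for >48 hours". Both sections cite the same core outcome set. Section 2.10.1 also describes the 48-hour follow-up in terms of extubation.

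**Weaning.** Under 2.9.2.5, when P_high reaches 10-12 cmH2O the APRV "patient can be transitioned to CPAP 10-12 cmH 2 O without pressure support", and extubation checks follow on those settings. This route avoids "pressure support ventilation, which is the weaning mode most commonly used as standard care". The same section also requires APRV to continue up to extubation. Control weaning (2.9.3.1) follows site practice: "low level pressure support, CPAP or T-Piece".

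**Schedule (3.1).** The "Primary outcome" row is marked up to CCU discharge.

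**The concern.** The two definitions give different stop times for the same patient, so one dataset can yield two primary results and sites cannot know which time to enter.

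The disagreement falls at the step where the arms are weaned differently. Time on pressure support counts as ventilated. Time on CPAP with no pressure support, read literally under 2.4.3, does not. If APRV patients spend more of their last intubated hours on CPAP than controls do, part of a measured difference could be reclassified tube time and not earlier liberation.

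The trial is open label, and 2.10.1 relies on this outcome being objective. Section 2.9.1 also describes the inspiratory phase of APRV as a CPAP phase, so under the literal reading the recorded stop could depend on when staff relabel the mode.

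**Working it through.** **Step 1. Compare the definitions by patient state**

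| State | 2.4.3, read literally | 6.2.3.2 |
|---|---|---|
| Intubated, pressure support | ventilated | ventilated |
| Intubated, CPAP, PS = 0 | finished, if still unassisted at 48 h | still ventilated (not extubated) |
| Extubated, mask CPAP | finished | arguably not finished (non-invasive support) |
| Extubated, high-flow oxygen | finished | not stated |

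The 48-hour condition does not remove the gap. A patient who moves to CPAP, is extubated some hours later and stays unassisted meets 2.4.3 from the CPAP switch. The stop times then differ by the intubated CPAP time.

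**Step 2. Reproduce the design target (6.1)**

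Inputs from 6.1: control median 9 days, reduction 2 days, power 90%, significance 5%, loss 5%. Assumed: exponential times, a two-sided test and an event in every evaluable patient.

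- Hazard ratio h = 7/9 (expressed as the ratio of medians).
- Freedman events = (1.960 + 1.282)² × [(1 + h)/(1 − h)]² = 10.507 × 8² = 672.5, so 673.
- 673/0.95 = 708.4, so 709, or 710 as 355 per arm. This matches the plan.
- Evaluable per arm: 355 × 0.95 = 337.

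The sample size is not in dispute. It sets the scale: for a liberated patient, 24 h of uncounted time is half of the 2-day target.

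**Step 3. Hypothetical size**

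The documents give no duration for the CPAP step, so this is an assumed range. The model has 337 per arm, exponential times with median 9 days in both arms and no true effect. Deaths are 30-40% of end points (1.1 cites mortality of about 40%) and are not shifted. Liberated patients have c hours removed. The test is a log-rank test, counting z > 1.96 in favour of APRV (nominal 2.5%), with 10,000 runs per cell. Ranges run from 40% to 30% deaths.

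| Gap c | APRV only | APRV, and half of liberated controls |
|---|---|---|
| 6 h | 3.2-4.0% | 2.9-3.0% |
| 12 h | 4.5-5.5% | 3.5-3.6% |
| 24 h | 8.8-10.2% | 4.6-5.4% |
| 48 h | 20.9-26.9% | 8.5-9.8% |

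With 40% deaths, a 24 h APRV-only gap gives an apparent mean difference of about 0.6 × 1 day = 0.6 days (simulated 0.59). Log-normal times (log SD 0.8, 40% deaths, 3,000 runs) give somewhat larger APRV-only rates: 3.8%, 6.1%, 11.6% and 30.4%.

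**The case against.** The strongest reply is that 2.4.3 already counts invasive ventilation without qualification. Only the non-invasive item is limited to volume or pressure support. The exclusion pairs CPAP with high-flow oxygen, so it can be read as removing non-invasive modes only. On that reading an intubated patient on ventilator CPAP is still invasively ventilated, which agrees with the extubation wording in 6.2.3.2 and 2.10.1. This is a tenable reading, but 2.4.3 does not state it, and CPAP with no pressure support does meet its test of no inspiratory support.

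Three further points limit the concern:

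- The CPAP step is permissive, is tied to extubation checks, and stands beside the requirement to continue APRV until extubation. It may last only hours, and at about 6 h the effect is small.
- Controls may wean on CPAP or T-piece, which the literal reading would treat the same way. Any asymmetry is one of degree.
- Time to first extubation is already a secondary outcome and would reveal a discrepancy. It would not correct the primary result.

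A reader might also infer that a tracheostomised patient has no end point under 6.2.3.2. That does not hold, because its operative wording is freedom from ventilatory support, which can be applied to such a patient. Nor does the schedule lose the outcome in general: only patients who leave the CCU within 48 h of liberation are affected, and the protocol's CCU includes high-dependency units.

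**Conclusion.** The protocol is wrong as written. One primary outcome has two end points that disagree on intubated CPAP and arguably on mask CPAP, and the primary result depends on which is applied. This needs correcting whatever the size of any bias.

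A reader might go further and infer that the definition alone makes the clock stop earlier under APRV. The documents do not support that. It requires the literal reading of 2.4.3, use of the permitted CPAP step for a material time, and less CPAP or T-piece weaning in controls. The first is contestable, the second is not quantified, and the third rests on one general remark in 2.9.2.5 about usual care.

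The false-positive rates are therefore illustrations. They run from little above nominal at 6 h to 21-27% if every liberated APRV patient has 48 h of uncounted CPAP and no control has any. If half of liberated controls have the same gap, the range is about 3% to 10%.

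**What to change.** - Use one definition in 2.4.3, 2.9.4.2, 6.2.3.2 and the eCRF, applied identically in both arms.
- For the primary outcome, count CPAP delivered by the ventilator through an endotracheal or tracheostomy tube as ventilated time. State that mask CPAP and high-flow oxygen after extubation do not count, in line with 2.4.3. State in the same place how T-piece time is counted, with the same rule for both tube types.
- Record the date and time of the first switch to CPAP with zero pressure support in both arms. Report the literal 2.4.3 reading, with the clock stopping at that switch, as a sensitivity analysis.
- Make clear in the schedule (3.1) that the 48-hour check is completed for patients who leave the CCU within 48 h of liberation.
- The sponsor should reconcile the two statements in 2.9.2.5 about CPAP before extubation and APRV until extubation. Nothing here requires a change to the weaning rules.

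The cost is protocol and eCRF wording, one extra time stamp, and a small clarification of the core-outcome wording. The sensitivity analysis keeps comparability with the literal reading. The time stamp should be added early, because the switch may be hard to recover consistently if it is not recorded at the time.
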